aspects of SBRT planning that differ among institutions and protocols and limit comparison of results include: a) selection of patients (often not clearly described); b) how patients are simulated (and particularly how respiratory motion is assessed, accounted for and/or controlled); c) how the target volumes are outlined (GTV alone or with a margin for CTV); d) how the plan is generated (only co-planar beams or also non-co-planar, lung heterogeneity correction or not; if yes, what correction algorithm is being used); e) where the prescribed dose is defined (which isodose is chosen and how, what amount of GTV is covered by the prescription dose); and f) what doses are allowed for the organs at risk. Just as important and just as much a source of variability, are the different aspects of SBRT delivery process: how are the patients immobilized; how are the stereotactic coordinates defined and assured; what quality of image guidance is used; and how to assure that patients will not move during the (often long) treatment time of large fraction SBRT treatment.

In addition to these technical aspects, another critical factor in being able to confidently apply the information from the literature is whether patients have been followed rigorously and for long enough, as both primary tumor control and toxicity are expected to, and indeed have been demonstrated to get worse with longer follow up. Therefore, formal prospective studies, particularly with an independent data safety monitoring committee, are more reliable than a single institution retrospective review of that institution's SBRT experience. This is especially true for studies that include patients who are frail or have significant co-morbidities, as these patients may be more likely to be lost to follow up or to have their symptoms attributed to their other illnesses. Thus, despite emerging reports in the literature on the results of SBRT for early stage NSCLC, it is still not clear which schedules are best in terms of tolerable toxicity and highest rates of primary tumor control.

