### PFT (FEV-1, FVC, DLCO) Decline

## **6.10 Radiation Therapy Adverse Event Reporting**

### **6.10.1 Adverse Events (AEs) and Serious Adverse Events (SAEs) Reporting Requirements** Adverse events (AEs) as defined in the tables below and all serious adverse events (SAEs) will be reported to the Cancer Therapy Evaluation Program (CTEP) via the Adverse Event Expedited Reporting System (AdEERS) application as directed in this section.

**Definition of an AE:** Any unfavorable and unintended sign (including an abnormal laboratory finding), symptom, or disease temporally associated with the use of a medical treatment or procedure regardless of whether it is considered related to the medical treatment or procedure (attribution of unrelated, unlikely, possible, probable, or definite). [CTEP, NCI Guidelines: Adverse Event Reporting Requirements. January 2005; <http://ctep.cancer.gov/reporting/adeers.html>]

**Definition of an SAE:** Any adverse experience occurring during any part of protocol treatment and 30 days after that results in any of the following outcomes:

- Death;
- A life-threatening adverse experience;
- Inpatient hospitalization or prolongation of existing hospitalization;
- A persistent or significant disability/incapacity;
- A congenital anomaly/birth defect.

Important medical events that do not result in death, are not life threatening, or do not require hospitalization may be considered an SAE experience, when, based upon medical judgment, they may jeopardize the patient and may require medical or surgical intervention to prevent one of the outcomes listed in the definition.

Pharmaceutically supported studies will require additional reporting over and above that which is required by CTEP.

SAEs (more than 30 days after last treatment) attributed to the protocol treatment (possible, probably, or definite) should be reported via AdEERS.

**Note: All deaths on study require both routine and expedited reporting regardless of causality. Attribution to treatment or other cause must be provided. "On study" is defined as during or within 30 days of completing protocol treatment.**

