## 6.10.2 **SPECIAL REPORTING FOR THIS STUDY**

Immediately upon identification of a serious adverse event (SAE) as defined in Section 13.1.1 and provided below), the site will telephone the 24-hour RTOG AE Report Line: [contact]. The site will provide details of the SAE to RTOG Headquarters and will be instructed to fax the completed lung adverse event form (AE), [contact] within 24 hours of discovery of the adverse event. The AE form is available on the RTOG web site, with all of the 0813 forms. The site also will report the adverse event via AdEERS (see Section 6.10).

All reported adverse events will be reviewed by 1 of 3 designated radiation/medical oncologists not associated with this study within 2 business days of receipt of all supporting documentation. The determination of those adverse events as a study DLT will be made by the designated independent reviewer.

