### **RTOG REPORTING REQUIREMENTS (7/27/10)**

AdEERS provides a radiation therapy (RT)-only pathway for events experienced involving RT only, both with and without a drug component arm. Events that occur on the RT-only arm of a study with a drug component must be reported for purposes of comparison. Events that occur on an RT-only study without a drug component also must be reported. Events involving RT-only must be reported via the AdEERS RT-only pathway.

The descriptions and grading scales found in the revised NCI Common Terminology Criteria for Adverse Events (CTCAE) version 4 will be utilized for AE reporting beginning October 1, 2010. All appropriate treatment areas should have access to a copy of the CTCAE version 4. A copy of the CTCAE version 4 can be downloaded from the CTEP web site, <http://ctep.cancer.gov>.

**Adverse Events (AEs) and Serious Adverse Events (SAEs) that meet the criteria defined above** experienced by patients accrued to this protocol **must be reported via AdEERS. SAEs must be reported within 24 hours of discovery of the event. Contact the CTEP Help Desk if assistance is required.**

**All supporting source documentation being faxed to NCI, must be properly labeled with the RTOG study/case numbers and the date of the adverse event and must be faxed to the RTOG dedicated AE/SAE FAX, [contact], before the 5- or 10-calendar-day deadline. All forms submitted to RTOG Headquarters also must include the RTOG study/case numbers;** non-RTOG intergroup study and case numbers must be included, when applicable. AdEERS Reports are forwarded to RTOG electronically via the AdEERS system. Use the patient's case number as the patient ID when reporting via AdEERS.

Any late death (more than 30 days after last treatment) attributed to the protocol treatment (possible, probable or definite) should be reported via AdEERS within 24 hours of discovery. An expedited report, if applicable, will be required within 5 or 10 calendar days.

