**Image-Guided Therapy Center (ITC)**

**ATTN: [name]**

**[name]**

**St. Louis, MO 63108**

**[contact]**

**[contact]**

**13.0 STATISTICAL CONSIDERATIONS**

**13.1 Study Endpoints**

**13.1.1** Primary Endpoint of Phase I Portion (7/27/10)

The maximal tolerated dose (MDT) of SBRT radiation dose associated with a 0.20 probability of dose-limiting toxicity (DLT); DLT is defined as any grade 3 or worse toxicity (per CTCAE, v.4, MedDRA, v. 12.0), that occurs within 1 year from the start of SBRT, is possibly, probably, or definitely related to treatment, and is related to the following specific symptoms:

- Grade 3-5 Cardiac Disorders
  - Pericardial effusion
  - Pericarditis
  - Restrictive cardiomyopathy
- Grade 4-5 Gastrointestinal Disorders
  - Dysphagia
  - Esophagitis
  - Esophageal fistula
  - Esophageal obstruction
  - Esophageal perforation
  - Esophageal stenosis
  - Esophageal ulcer
  - Esophageal hemorrhage
- Grade 3-5 Nervous System Disorders
  - Brachial plexopathy
  - Recurrent laryngeal nerve palsy
  - Myelitis
- Respiratory, Thoracic, and Mediastinal Disorders, Grade 3-5, except as noted below
  - Atelectasis (grade 4-5 only)
  - Bronchopulmonary hemorrhage
  - Mediastinal hemorrhage
  - Pleural hemorrhage
  - Tracheal hemorrhage
  - Bronchial fistula
  - Pulmonary fistula
  - Bronchopleural fistula
  - Tracheal fistula
  - Hypoxia (provided grade 3 is worse than baseline)
  - Bronchial obstruction
  - Tracheal obstruction
  - Pleural effusion
  - Pneumonitis
  - Pulmonary fibrosis

- Changes in Pulmonary Function Tests per the SBRT Pulmonary Toxicity Scale (see Section 6.9.5), Grade 3-5
  - FEV1 decline
  - Forced Vital Capacity decline
- Any Grade 5 adverse event attributed to treatment

All reported serious adverse events (SAEs) listed above will be reviewed by 1 of 3 designated senior radiation/medical oncologists who have expertise in the treatment of lung cancer and who are not associated with this study within 2 business days of receipt of all supporting documentation. The determination of those SAEs as a study DLT will be made by the designated independent reviewer. All reported SAEs listed above will be considered DLTs until reviewed by the designated independent reviewer.

**13.1.2** Primary Endpoint of Phase II Portion (8/20/10)

Two-year primary tumor control rate at the MTD of SBRT (See Section 11.3.3)

**13.1.3** Secondary Endpoints

**13.1.3.1** Progression-Free Survival (see Section 11.3.3);

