The goal of the trial is to determine the fraction size (dose) for SBRT most closely associated with a 0.20 probability of a DLT (specified as the *target rate*). As patients present for enrollment, they are assigned the highest dose associated with an estimated probability of a DLT less than or equal to the target rate of 0.2. The initial estimates of the probability of a DLT at each dose (column 3 of Table 13.1) are updated with the accumulated patient information using a Bayesian paradigm so that the estimation of the target dose, and, thereby, the assignment of the next dose, is based upon all the information available at the time of enrollment. To allow the trial to remain open to new patient entries without pause, while using the maximum available information, data from patients who have been enrolled but have not completed the 1 year observation period are weighted according to the proportion of the observation period the patient has completed (data from patients who have experienced a DLT are fully weighted).

**Table 13.1:** Toxicity probability estimates of trial design and simulation assumptions used to determine operating characteristics

Dose Level	SBRT Fraction Dose (Gy)	Probability of Toxicity			
		Design ( $p_0$ )	Scenario		
			DLT per trial design (DLT-td)	DLT+	DLT++
1	8.0	0.01	0.01	0.02	0.02
2	8.5	0.02	0.02	0.04	0.05
3	9.0	0.04	0.04	0.06	0.08
4	9.5	0.05	0.05	0.10	0.13
5	10.0	0.08	0.08	0.15	0.18
6	10.5	0.10	0.10	0.20	0.30
7	11.0	0.14	0.14	0.30	0.40
8	11.5	0.17	0.17	0.35	0.60
9	12.0	0.20	0.20	0.45	0.80

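### A death between 30 days after SBRT and 12 months, coded to a cause not on the DLT list, is listed for independent DLT review only if attributed to treatment; a missed one biases the MTD upward

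*Protocol*

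**What the plan says.** Section 13.4.1 seeks the dose "most closely associated with a 0.20 probability of a DLT". Section 13.1.1 counts an event as a DLT if it "occurs within 1 year from the start of SBRT, is possibly, probably, or definitely related to treatment, and is related to the following specific symptoms". The list that follows names organ-specific terms and closes with "Any Grade 5 adverse event attributed to treatment". Section 6.10.2 repeats the list as the events that need special reporting.

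On review, the two sections differ:

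- Section 6.10.2: "All reported adverse events will be reviewed by 1 of 3 designated radiation/medical oncologists not associated with this study".
- Section 13.1.1 confines review to the serious adverse events on its list and adds: "All reported SAEs listed above will be considered DLTs until reviewed by the designated independent reviewer".

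On deaths, Section 6.10.1 requires reporting whatever the cause only during treatment or in the 30 days after it. For later deaths, the RTOG reporting requirements say: "Any late death (more than 30 days after last treatment) attributed to the protocol treatment (possible, probable or definite) should be reported via AdEERS".

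Under Section 13.3, a patient who completes treatment and dies of something other than toxicity does not count towards the 75 evaluable patients. That patient's data are still used for dose allocation and the final toxicity analysis, weighted by the proportion of the observation period completed.

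**The concern.** The DLT window runs for 12 months, but reporting of deaths regardless of cause stops 30 days after treatment. For the rest of the window, a death coded to infection, cardiac or respiratory failure, or left unexplained, is on the lists of Sections 6.10.2 and 13.1.1 only if somebody has already attributed it to treatment. The protocol does not say who. The site knows the assigned dose.

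The protocol's own background makes this more than a formality. Section 1.2 says of frail patients that "these patients may be more likely to be lost to follow up or to have their symptoms attributed to their other illnesses", and eligibility requires severe comorbidity. In the earlier single-institution phase II study described there, six patients may have had grade 5 toxicity. Four of the six deaths were infectious pneumonia, which is not a listed DLT term, and the six deaths came at a median of 10.4 months after SBRT.

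At stake is the phase I primary endpoint. A toxic death that is not recognised loses its full weight as a DLT and is counted as DLT-free time instead, so both dose assignment and the final MTD move up.

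**Working it through.** **1. Route of a death at month 8, by coded cause**

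| Coded cause | Special-reporting list, 6.10.2 | DLT until reviewed, 13.1.1 |
|---|---|---|
| Listed term (e.g. bronchopulmonary hemorrhage, pneumonitis, pericardial effusion) | Yes, no attribution condition in the list | Yes |
| Unlisted cause, attributed to treatment | Yes, by the closing item | Yes |
| Unlisted cause, not attributed | Not listed | No |

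Only the last row is exposed. The rule for phase I studies in the AdEERS section (grade 4 and 5 serious events whatever their relationship) does not cover it, because Section 6.10.1 limits a serious event to treatment plus 30 days. Later events need attribution.

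**2. What the model does with it**

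Section 13.4.1 gives p(d) = exp(3 + αd) / (1 + exp(3 + αd)), with d = log(p0/(1 − p0)) − 3, α ~ N(1, 0.3), and weight w = u/12 without a DLT. In the usual TITE-CRM likelihood a DLT contributes p and DLT-free follow-up contributes 1 − wp. For a death at month 8, w = 8/12 = 0.67. At p = 0.20 the contribution is 1 − 0.67 × 0.20 = 0.87 instead of 0.20.

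**3. Reproducing the plan's figures**

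Entries: 75/0.80 = 93.75, rounded up to 94. At 2 per month, 94/2 = 47 months, about the stated 4 years.

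The design was rebuilt with the start at Level 5, one-level escalation after 12 patient-months at the current level, target 0.20, 75 patients, accrual of 2 per month and 1,000 trials per setting. With a flat hazard and nothing missed:

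| Quantity | Protocol | Rebuild |
|---|---|---|
| Design scenario (DLT-td), under 15 DLTs | over 85% | 91% |
| DLT-td, under 18 DLTs | at least 99% | 99.4% |
| DLT+, within one level of target | over 90% | 94% |
| DLT+, Level 6 selected | about 40% | 45% |
| DLT+, Level 8 / Level 9 selected | about 4.5% / 1.0% | 2.9% / 0.2% |

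**4. The missed share (an assumption; the documents give none)**

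The earlier study had 8 patients with grade 3–4 and 6 with possible grade 5 events, 14 if no patient is in both groups. Two of the six deaths, from hemoptysis and pericardial effusion, correspond to listed terms. Four do not.

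- One in three of those four missed: (4/14) × (1/3) = 0.095, about 10%.
- All four missed: 4/14 = 0.286, about 29%.

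The second is an upper case. The deaths ranged from 0.6 to 19.5 months, so at least one fell within about 18 days (0.6 × 30.4) and at least one after month 12. At most four of the six therefore lie in the exposed period.

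**5. Effect on the declared MTD (flat hazard)**

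| Share of DLTs missed | DLT+: mean true P(DLT) at MTD | DLT+: chance true P ≥ 0.30 | DLT++: mean | DLT++: chance |
|---|---|---|---|---|
| 0 | 0.214 | 27% | 0.207 | 30% |
| 10% | 0.238 | 42% | 0.227 | 41% |
| 20% | 0.260 | 55% | 0.251 | 54% |
| 29% | 0.294 | 73% | 0.283 | 69% |

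Under DLT-td the mean goes from 0.185 to 0.198 at 29% missed, and no trial selects a dose above target, because Level 9 is both the top level and the true target.

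The Monte Carlo standard error at 42% is √(0.42 × 0.58/1000) = 1.6 points. Missed deaths were kept among the 75 patients and other non-toxic deaths were not simulated, which is a simplification.

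**The case against.** A reader might infer that every late death escapes independent review unless the site has blamed the treatment. The text does not support that. The organ-specific items in the Section 6.10.2 list carry no attribution condition, must be telephoned in at once and faxed within 24 hours, and count as DLTs until reviewed. A fatal pneumonia may also reach review through grade 3–5 hypoxia or pleural effusion, both listed, although nothing requires the site to code those terms separately.

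The strongest reply goes further. Section 6.10.1 defines an adverse event regardless of attribution, Section 12.1 asks for the adverse event form within 24 hours of identification and again at 12 months, and Section 6.10.2 says all reported adverse events are reviewed. On that reading an unattributed late death does reach the independent oncologist. This is a fair reading, but Section 13.1.1 limits review, and the default to DLT, to listed serious events. What stands is an unresolved conflict, not a proven exclusion.

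Two other inferences fail. The protocol nowhere says that the site makes the attribution of a death; it is silent. Nor is the independent determination the only safeguard: the data safety monitoring board reviews the trial twice a year and as needed, although it is given no part in classifying DLTs. Where attribution does apply, a possible relation is enough.

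The earlier study is also a loose guide to size. It used three fractions, took tumors anywhere in the lung, and described its grade 5 events only as potential.

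**Conclusion.** The point holds in a narrow form. For deaths from 30 days after treatment to month 12 with a cause not on the DLT list, the protocol contradicts itself on whether the independent oncologist sees them, and its special-reporting and DLT lists include them only once attributed. A toxic death missed in this way counts as DLT-free follow-up of weight u/12, so the direction of bias is certain: upward.

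The size is not certain. It rests on an assumed missed share of 10% to 29%, on a flat hazard, and on the true toxicity being as in DLT+ or DLT++. Under those conditions the chance of an MTD with true P(DLT) of 0.30 or more rises from 27% to between 42% and 73% (DLT+), or from 30% to between 41% and 69% (DLT++). If the design's own toxicity curve is right, no over-target dose is declared. The harm thus arises when SBRT is more toxic than assumed, which is when the phase I part most needs to be reliable. This is a cheap improvement worth making, not evidence that the design fails.

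**What to change.** In Sections 6.10.2 and 13.1.1, require every death within 12 months of the start of SBRT to go to the existing independent reviewer whatever attribution the site has given, and state that the reviewer's attribution decides DLT status. Reconcile these sections with the 30-day rule in Section 6.10.1, the RTOG reporting requirements and the wording on non-toxic deaths in Section 13.3. The DLT definition stays as it is.

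The cost is a short amendment and at most about 94 − 75 = 19 extra review packages, if every projected non-evaluable entry were a death. If pending deaths are handled as Section 13.1.1 already handles listed events, some unrelated deaths will count provisionally as DLTs. The two-business-day review clock starts only when all supporting documents have arrived, and no deadline for sending them is set, so one should be added. Up to 19 provisional DLTs is not small beside the 11 to 18 median DLTs per trial that the protocol projects, and their temporary effect on dose assignment has not been simulated.

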These scenarios are used to assess the robustness of the design to mis-specification of the probabilities of toxicity. The trial assumes that a patient has the same risk of developing a DLT at any point during the 1-year observation period (flat hazard rate). Because of this, the cumulative observation time across patients is acceptable. Within each scenario, this assumption is tested by assessing the operating characteristics of trials where: DLT is equally likely across 1 year (trial assumption); DLT is substantially more likely early in the trial; DLT is substantially more likely late in the trial (see insets, Figure 13.1 below). In 2 completed RTOG trials, 0236 and 0324, which used CTCAE, v. 3.0, the timing of the DLTs as defined in this study was examined during the first year. In both trials, there was no suggestion that the DLTs were more likely to occur later in the risk period. (see Appendix VII for further details). Two hundred and fifty trials were simulated for each of the nine sets of experimental conditions derived from the 3 scenarios and the 3 different hazard rates. The numbers of DLTs, estimated target doses, distribution of doses, and statistical power to identify at least 1 dose as possibly being superior to standard therapy are graphed in Figures 13.1 and 13.2 (below).

**13.2.1** Expected Number of Observed DLTs

The distributions of the number of DLTs observed (out of 75 treated and evaluable patients) for the simulated trials are described in the box plots in Figure 13.1. The boxes indicate the 75th, 50th, and 25th percentiles (from top to bottom), and the stems extend to the 95th and 5th percentiles. The plus indicates the mean. The median number of DLTs ranges from 11 (14.7%) to 18 (24%). If the design assumptions about P(DLT) are correct (DLT-td), over 85% of the simulated trials have less than 15 DLTs (20%), and at least 99% have less than 18, irrespective of the hazard rate. If P(DLT) is under-estimated as in scenarios DLT+ and DLT++, the median number of toxicities for simulated trials in either scenario does not exceed 18, and

the third quartile does not exceed 20 (26.7%). The number of toxicities observed is relatively insensitive to the mis-specification of the hazard rate.

[figure not shown]
**13.2.2** Accuracy of Selection of Target Dose

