The distributions of target doses that the trial selects are presented in the right column of Figure 13.1. If the design assumptions about P(DLT) are correct (DLT-td), the trials overwhelmingly pick the correct target dose, indicated by the asterisk (Level 9). If P(DLT) is underestimated as in scenario DLT+ , the target dose is picked within one level of the true target dose (i.e., with  $0.15 \leq P(\text{DLT}) \leq 0.30$ ) in over 90% of the simulated trials. If the P(DLT) is more severely underestimated as in scenario DLT++ , that proportion is higher.

[figure not shown]
**13.2.3** Estimation of Primary Tumor Control (8/20/10)

The average number of patients treated at each dose is displayed in the left column of Figure 13.2. Again, the target dose is denoted by an asterisk. In the DLT-td cases, 7-14 patients are treated at Levels 5-8 due to the starting dose (level 5, 10 Gy) and escalation restrictions. In the DLT+ simulations, 8-14 patients on average are treated on either of the 2 dose levels (8 and 9) with  $P(\text{DLT}) > 0.3$ , which result, on average in 3-5 DLTs. In the DLT++ simulations, 8-15 patients on average are treated on 1 of 3 dose levels (7, 8, and 9) with  $P(\text{DLT}) > 0.3$  which result on average in 4-8 DLTs.

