### **13.3 Sample Size (8/20/10)**

This trial will accrue 75 patients fully evaluable for the DLT toxicity analysis.

Monte Carlo simulation was used to assess the operating characteristics of this design. Complete trials (2,250 for each trial scenario considered) were simulated using 3 different assumptions about the true probabilities of dose-limiting toxicity at each dose: 1) as assumed; 2) somewhat more toxic than assumed; 3) more toxic than assumed with significant increase in toxicity between doses 6 and 7. Among the operating characteristics considered in the sample size were the expected number of dose-limiting toxicities, the probability of selecting the correct dose (that associated with a 20% probability of DLT) as the target dose at the end of the trial, the time required to complete the trial, and the number of patients treated at or near the target dose. Sample sizes from 30 to 120 were evaluated, as were different rates of patient accrual. A sample size of 75 patients was determined to have acceptable probability of correctly selecting a dose with acceptable toxicity and enough patients treated about the target dose for characterization of the efficacy endpoints, while being feasible for completion of accrual within 4 years.

A patient is fully evaluable for toxicity analysis if:

1. The patient fails to complete treatment due to a DLT.  
OR
2. The patient receives all five RT fractions of the protocol treatment.  
AND
  - A. Experiences a DLT within 1 year from the initiation of treatment  
OR
  - B. Is observed per protocol for 1 year after the initiation of treatment and does not experience a DLT

Patients who complete protocol treatment but have progressive disease and no DLT within 1 year are still considered at risk for a DLT even if they receive chemotherapy. It is not likely that the addition of chemotherapy will greatly affect the occurrence of a SBRT-related DLT, and we did not want to exclude patients at risk of DLT.

A patient who does not complete protocol treatment because of non-protocol, treatment-related toxicity; non-protocol, treatment-related death; or refusal to complete protocol treatment will not be evaluable.

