Patients who complete protocol treatment but cannot be observed for a DLT for 1 year (e.g., due to death from other than toxicity or patient refusal) will not count towards the accrual goal, but their data will be used to allocate doses to subsequent patients and in the final analyses for toxicity, primary tumor control and survival, they will be weighted, as appropriate, by the proportion of the observation period they have completed. Note: Patients, who have experienced a DLT, are fully weighted.

It is anticipated that average accrual will be 2 patients per month. Based upon RTOG 0236 (another RTOG trial utilizing SBRT), it is projected that 80% of patient entries will be evaluable for DLT analysis. So to accrue 75 evaluable patients, a total of **94 patients** will have to be entered, and this will take 4 years to complete.

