### **13.4 Allocation of Participants to Doses**

#### **13.4.1 The Weighted Dose-Toxicity Model**

Doses will be allocated to patients by means of the Time-to-Event Continual Reassessment Method (TITE-CRM) Phase I trial. A logistic dose-toxicity model was used for this trial with rescaled dose  $d = (\log(p_0 / (1-p_0)) - 3)$ .

$$p(d) = e^{3+ad} / (1 + e^{3+ad}), \text{ (eq. 1)}$$

In the logistic dose-toxicity model, the prior distribution of the dose-toxicity parameter  $\alpha$  is Gaussian with mean 1 and standard deviation of 0.3 which is based upon experience with other trials using this model.  $\alpha=1.0$  represents our initial assumption about the toxicity of treatment, as displayed in the third column of Table 13.1

The weight function reflects the amount of information available from a patient. If a DLT is observed, the full information from this patient is available and the weight will be 1. Otherwise, the uniform weight function ranging from 0 to 12 months will be used. Each patient will be followed for DLT until the patient either reaches one year (12 months) from the start of SBRT without experiencing a DLT or experiences a DLT, whichever comes first. Let the time to a DLT of patient be  $U_i$ , then the weight function,  $w(u) = u/12$ .

This is translated into the following:

- A) Patients who have enrolled in this trial but have not experienced a DLT have a weight equal to the proportion of the 12 months observation period they have completed.
- B) Patients who have experienced a DLT before 12 months from the start of SBRT or complete protocol treatment without a DLT have a full weight, 1.

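### Section 13.2.2 overstates dose-selection accuracy: when the design is right, Level 9 is chosen in about two trials in three, not overwhelmingly

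*Protocol*

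**What the plan says.** Section 13.2.2 describes the selected doses shown in Figure 13.1. For DLT-td, where the true probabilities equal the design probabilities and Level 9 is the true target, it says "the trials overwhelmingly pick the correct target dose". For DLT+ it gives a number: over 90% of trials within one level of the target. For DLT-td it gives none in the text.

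Section 13.5.1.1 makes the MTD the dose whose P(DLT) is closest to 0.20. Section 13.4.2 assigns each new patient by a different rule, the highest level with expected P(DLT) at or below 0.20.

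Section 13.3 states: "This trial will accrue 75 patients fully evaluable for the DLT toxicity analysis". It lists the probability of selecting the correct dose among four operating characteristics considered for that number.

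On replicates, Section 13.2 says "Two hundred and fifty trials were simulated for each of the nine sets of experimental conditions"; Section 13.3 says "2,250 for each trial scenario considered".

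**The concern.** Table 13.1 sets Level 8 at 0.17 and Level 9 at 0.20 under DLT-td. Even if every patient were treated at Level 9, the standard error of the observed DLT proportion would be sqrt(0.20 × 0.80 / 75) = 0.046, or 4.6 points. The model has to separate two levels three points apart with that precision, so near-certain selection of Level 9 is implausible.

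The statement matters because it is the only description in the text of selection accuracy when the design is correct, and that property is one of those considered for the sample size. The phase II test is made only at the selected MTD (Section 13.5.1), so a reader needs to know how often that dose will be below the true target.

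**Working it through.** **Inputs**

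- Model (Section 13.4.1): p(d) = exp(3 + αd) / (1 + exp(3 + αd)), with d = logit(p0) − 3. The prior on α "is Gaussian with mean 1 and standard deviation of 0.3".
- Weights (Section 13.4.1): 1 after a DLT. "Otherwise, the uniform weight function ranging from 0 to 12 months will be used", so w = u/12.
- Probabilities, Levels 5 to 9 under DLT-td (Table 13.1): 0.08, 0.10, 0.14, 0.17, 0.20.
- Allocation (Section 13.4.2): start at Level 5, rise at most one level at a time, and only after one year of cumulative observation at the current level.
- Final rule (Section 13.5.1.1): P(DLT) closest to 0.20.
- Accrual (Section 13.3): "It is anticipated that average accrual will be 2 patients per month"; 75 evaluable patients.
- Assumed: the early and late hazard shapes are drawn only in a figure that is not shown. Beta(1,3) and Beta(3,1) on 0-12 months were used. The flat hazard needs no such assumption.

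**Step 1. Check against the protocol's own figures (flat hazard, expected α plugged into the model, 1,000 trials).**

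| Quantity | Protocol | Rebuilt |
|---|---|---|
| Median DLTs, DLT-td | lowest stated median 11 | 11 |
| Trials with <15 DLTs, DLT-td | over 85% | 91.6% |
| Trials with <18 DLTs, DLT-td | at least 99% | 99.8% |
| Mean patients at each of Levels 5-8, DLT-td | 7-14 | 8.2, 11.9, 12.8, 12.9 |
| Within one level, DLT+ (closest rule) | over 90% | 22.8 + 48.4 + 24.2 = 95.4% |

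The match is partial elsewhere. Under the assumed late hazard, 83.4% of DLT-td trials have <15 DLTs (stated over 85%), and the DLT++ median is 20 (stated maximum 18). Under the assumed early hazard the DLT-td median is 10. Mean patients at Levels 8-9 under DLT+ are 5.3 + 2.5 = 7.8 (flat), 2.3 + 0.6 = 2.9 (early) and 9.8 + 7.2 = 17.0 (late), against a stated 8-14.

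**Step 2. Selection under DLT-td, closest rule (1,000 trials each).**

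| P(DLT) estimate | Hazard | Level 8 | Level 9 | Levels 8 + 9 |
|---|---|---|---|---|
| Plug-in expected α | flat | 19.2% | 69.4% | 88.6% |
| | early | 20.1% | 68.6% | 88.7% |
| | late | 20.0% | 69.9% | 89.9% |
| Posterior mean of P | flat | 22.3% | 64.6% | 86.9% |
| | early | 21.8% | 64.1% | 85.9% |
| | late | 20.6% | 67.1% | 87.7% |

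With the plug-in estimate and flat hazard (2,000 trials each), accrual of 1 or 4 per month gives 66.4% or 67.6% for Level 9. N = 94 gives 66.6% and N = 120 gives 67.6%. Prior SDs from 0.1 to 0.55 give 66.5-70.9%. Other runs with the posterior mean go down to 63%.

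**Step 3. Exact check without hazard, accrual or escalation assumptions.** Put all 75 patients at Level 9, fully observed, true P = 0.20. For each count x, compute the posterior mean of α, put it in the model and apply the closest rule.

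- x = 16: mean α = 0.987, p8 = 0.1785, p9 = 0.2092. Distances from 0.20 are 0.0215 and 0.0092, so Level 9.
- x = 17: mean α = 0.970, p8 = 0.1905, p9 = 0.2221. Distances are 0.0095 and 0.0221, so Level 8.

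Level 9 is therefore selected when x ≤ 16. P(X ≤ 16) for Binomial(75, 0.20) is **67.6%**. Counts 17 to 19 lead to Level 8: 9.3 + 7.5 + 5.6 = 22.4%. The two together are 90.0%.

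**Step 4. Simulation noise.** With 250 trials the standard error at 67.6% is sqrt(0.676 × 0.324 / 250) = 3.0 points, too small to explain the wording.

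**Step 5. Replicate count.** 9 × 250 = 2,250 in all, or 3 × 250 = 750 for each toxicity scenario.

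**The case against.** The adverb describes a figure that is not available here, and no printed number is wrong. Level 9 is chosen about three times as often as Level 8. Section 13.3 supports 75 patients by the chance of choosing a dose with acceptable toxicity, and under DLT-td every level has P(DLT) at or below 0.20, so a choice of Level 8 meets that aim. All of this stands, and it limits the point to a misdescribed property. It does not make 63-70% overwhelming.

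The rebuild also matches the stated figures only in part, and the early and late shapes are assumed. It cannot be said to reproduce the sponsor's simulation. The conclusion therefore rests on the flat-hazard runs and the exact check in Step 3, which need neither shape.

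Three stronger readings are tempting and are not supported:

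- *Level 9 is chosen only about half the time.* The highest-level-at-or-below-0.20 rule gives about 52-57%, but that rule assigns patients. The MTD is defined by the closest rule.
- *The stated power is therefore too high.* Section 13.2.3 describes power at the chosen target dose, so trials that select a lower level are already counted.
- *The replicate counts contradict each other and inflate Monte Carlo precision threefold.* If a trial scenario in Section 13.3 means one sample-size and accrual configuration, 3 toxicity × 3 hazard × 250 = 2,250 agrees with Section 13.2. If it means a toxicity scenario, the ratio of standard errors is sqrt(2,250/750) = 1.7. Threefold, sqrt(2,250/250), needs 2,250 per condition. The protocol text states no Monte Carlo error in any case.

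**Conclusion.** The statement is wrong as written. By the protocol's own MTD rule, Level 9 is selected in about 63-70% of trials when the design assumptions hold exactly, and in 67.6% under full observation of all 75 patients at that level. About 30-37% of trials select a lower level, mostly Level 8; Levels 8 and 9 together account for about 86-90%.

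This rests on the printed model, prior, weights and escalation rules, and on the closest-to-0.20 rule having been the one simulated, which Section 13.2.2 does not say. A reader might infer that the design or the sample size fails. It does not: Level 9 is the most frequent choice and most misses are one level low. Raising N to 120 leaves the figure at 67.6%, so more patients in that range would not cure it. The replicate count is an ambiguity of wording only.

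**What to change.** In Section 13.2.2, replace the adverb with the simulated percentage of DLT-td trials selecting Level 9 and the percentage selecting within one level, for each hazard shape. Name the final selection rule used in the simulations; it should be the rule in Section 13.5.1.1.

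As a minor clarification, state one replicate count in Sections 13.2 and 13.3, for example 250 per condition and 2,250 over the nine conditions. If Section 13.3 means each sample-size and accrual configuration, say so.

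The cost is a few restated figures from existing output, or a short re-run. The sample size, dose levels, allocation rule and analyses stay as they are.
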